## Feasibility Testing – Research Protocol

We propose to develop and examine feasibility of a tobacco cessation intervention tailored to persons living with HIV in Brazil. We already conducted Phase I (development and pre-testing of the intervention) among 14 participants. Phase II (current amendment) consists of the first iteration of the feasibility testing of the intervention. We will pilot test the tobacco cessation program among 10 persons living with HIV and who meet the inclusion criteria. We anticipate additional changes and adaptations as we pilot test the intervention among 10 participants. We will make adaptations based on their feedback to move to Phase III. The specific components of the intervention, number of sessions, format, etc will be determined in the pretesting phase. However, we anticipate being a mix of in-person, telephone, and WhatsApp contacts. We also anticipate being a mix of cognitive behavior therapy strategies and pharmacological aids. Based on additional feedback obtained in Phase II, we will pilot test the final intervention among 40 participants (Phase III). The specific components will be determined based on results of Phases I and II. If no changes are needed we will proceed enrolling the additional 40 participants in Phase II and Phase III will not be needed.

The primary outcome will be a 7-day point prevalence abstinence (defined as no tobacco use in the past 7 days and verified through measurement of *salivary cotinine and exhaled carbon monoxide (CO) levels*) at 7-month follow-up (from baseline).

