### **Feasibility Testing**

The intervention that was developed with input from the target audience during the pretesting phase consists of an initial comprehensive assessment (counseling + pharmacologic) since patients tend to come prepared to spend the day at the reference center to get all the needed services. If they are committed to quitting they will proceed with consenting, visits with the Clinical Psychologist and Pulmonologist. The four visits with the Clinical Psychologist can be in person, video or phone based on patient's preferences. Each patient is different and some may require more visits. The Clinical Psychologist will also provide the participant with the opportunity to send and receive texts for support. We will deliver the active intervention following this pattern for three months given the high risk of relapse within the first three months. Then, participants will continue to be engaged for another three months and monthly "check-ins" with the Clinical Psychologist and Pulmonologist. Follow-up assessments will be implemented at 7 months. The **cognitive-behavioral** component is based on evidence-based strategies but tailored to PLWH based on findings of the formative assessments. The tobacco cessation manual is available in Portuguese upon request.

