**Pharmacological management** will be consistent with the recommendations and aids available through the public health system in order to assure sustainability – nicotine replacement therapy (NRT) and bupropion (if needed). The optimal dose of NRT can be difficult to determine without evaluating tobacco use pattern, comorbidities, and context. Thus, the NRT dose will be determined based on this evaluation. For example, participants who smoke within 30 minutes of awakening or smoke more than 10 cigarettes daily may be offered a higher dose NRT. (61) Others will receive a lower dose therapy with the option of increasing the dosage if physical withdrawal symptoms persist at 2 weeks. Patches will be initiated one week prior to the quit date, will be administered for 8 weeks total and the dose will be either 21 mg (high dose) or 14 mg (low dose). The dose will not be tapered. Those with skin sensitivities will be offered the alternative of scheduled nicotine gum at 4mg or 2mg doses (which is also offered through the public health system). The appropriate course of treatment will be decided as a collaborative discussion between the participant and the Pulmonologist and the medication will be provided free of charge.

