### **Assessments**

Participants will be interviewer-administered baseline, post-test, and 7-month f/u assessments by the Research Assistant since the Clinical Psychologist will be delivering the intervention. Baseline measures will include (those with an \* will also be administered at post-test and 7-month f/u): demographics (e.g., age, income, etc.), tobacco history (e.g., # cigarettes per day, previous attempts, etc.), nicotine dependence\* (Fagerstrom Test for Nicotine Dependence), smoking self-efficacy\* (Smoking Self-Efficacy Scale), depressive symptoms\* (CES-D), and social support.\* These measures have been translated into Portuguese. Exhaled CO levels will be recorded at baseline, post-test, and 7-month f/u. Salivary cotinine will only be assessed at 7-month follow-up.

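### Does the primary abstinence outcome need stated cut-offs, and a rule for combining cotinine and exhaled CO, before it can be analysed?

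*Combined protocol and SAP*

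**What the plan says.** The opening section, Feasibility Testing – Research Protocol, sets the primary outcome as 7-day point prevalence abstinence at 7 months from baseline, "defined as no tobacco use in the past 7 days and verified through measurement of" "salivary cotinine and exhaled carbon monoxide (CO) levels". The Assessments section adds only timing. For CO: "Exhaled CO levels will be recorded at baseline, post-test, and 7-month f/u". For cotinine: "Salivary cotinine will only be assessed at 7-month follow-up". No section gives a threshold for either marker or says how a participant is classified when the two disagree.

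Three statements under Feasibility Testing bear on whether nicotine products could raise cotinine at 7 months:

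- On patches: "Patches will be initiated one week prior to the quit date, will be administered for 8 weeks total".
- The alternative for skin sensitivity is "scheduled nicotine gum at 4mg or 2mg doses (which is also offered through the public health system"), with no duration given.
- After three months of active intervention, "participants will continue to be engaged for another three months and monthly" check-ins with the psychologist and the pulmonologist take place.

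Sample Size and Statistical Analysis assumes 13% abstinence, quotes a 90% interval of 3.2% to 22.8% with 32 participants, recruits 40, and otherwise plans descriptive statistics.

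**The concern.** A biochemically verified outcome normally needs a threshold for each marker and a rule for joining them. Without these, two analysts could classify one participant differently. The awkward case is a person who reports abstinence, has CO below its threshold and has cotinine above its threshold.

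Cotinine is a metabolite of nicotine, so this pattern has two possible sources (a general property of the markers, not a figure from the documents). One is recent tobacco use that CO no longer shows. The other is a nicotine product used by someone who is tobacco-free. A rule requiring both markers counts both people as not abstinent; a CO-only rule counts both as abstinent.

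The trial itself supplies nicotine products, and this rate is the main quantity meant to inform a larger study. If the rule were open, it could be chosen after the data were seen. CO is also the only marker at post-test, so a both-markers rate at 7 months would differ in kind from any CO-verified rate at post-test.

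**Working it through.** **Inputs.** From Sample Size and Statistical Analysis: p = 0.13, n = 32, 90% confidence, 40 recruited. From Feasibility Testing: 8 weeks of patches, 3 months of active intervention, then 3 months of check-ins. From the research protocol section: sample at 7 months, look-back of 7 days.

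**1. Reproduce the plan's interval.** Margin = 1.645 × √(0.13 × 0.87 / 32) = 0.0978. Interval = 13% ± 9.8 points = 3.2% to 22.8%, as stated. Expected abstainers: 0.13 × 32 = 4.16.

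**2. Size of the ambiguity if the rule were truly open.** Let d be the number of self-reported abstainers with low CO and high cotinine. The two rules differ by d/32.

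| d | gap (points) | share of the 9.8-point margin |
|---|---|---|
| 0 | 0 | 0% |
| 1 | 3.1 | 32% |
| 2 | 6.2 | 64% |
| 3 | 9.4 | 96% |

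The documents give no value for d, so these rows are illustrations. It takes d = 4 (12.5 points) to exceed the margin, which is about the whole expected number of abstainers. Over all 40 recruited, each case would be worth 1/40 = 2.5 points.

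Example, using the plan's method:

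- 4/32 = 12.5%, with 90% interval 0.125 ± 1.645 × √(0.125 × 0.875 / 32) = 2.9% to 22.1%.
- With one of the four discordant, 3/32 = 9.4%, with interval 0.9% to 17.9%.

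The two intervals overlap almost entirely.

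**3. Is the rule open?** The outcome sentence joins cotinine and CO without ranking them. Cotinine is taken at one visit only, the one at which the primary outcome is assessed. Under a CO-only rule it would play no part in the outcome it is named to verify. The both-markers reading is the only one that gives each named measurement a role.

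**4. Could patches produce the discordance?** Seven months is 30.4 weeks.

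- A course started at baseline ends at week 8, which is 30.4 − 8 = 22.4 weeks before the sample.
- To reach into the last 7 days, a course must start after 30.4 − 1 − 8 = week 21.4.
- Active intervention ends at 3 months = week 13.0, so that start would come 21.4 − 13.0 = 8.4 weeks later.
- Check-ins run to 6 months = week 26.1, so a late start is not excluded, but no section describes starting a course at that stage.
- Gum has no stated duration, so late gum use is neither planned nor ruled out.

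**5. The cut-offs.** They are absent from the text. Their effect cannot be computed, because the documents give no marker distributions.

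**The case for a change.** The best case for a change runs as follows. A conjunction says what is measured, not how the results classify a person. Even if it means both markers, a negative result is undefined until thresholds are written, so the primary outcome cannot be reproduced from the plan alone. Treatment is individual ("The appropriate course of treatment will be decided as a collaborative discussion between the participant and the Pulmonologist"), no latest quit date is set, and recent smoking missed by CO gives the same discordant pattern without any nicotine product. Writing two or three sentences costs almost nothing, whereas sampling error at this size cannot be avoided.

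Part of this stands. The cut-offs are not in the text, and putting them on record before the first 7-month assessment would be tidy. They may already sit in assay or operating procedures outside these documents, though the text refers to none.

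The rest is weaker. Recent smoking missed by CO is exactly what cotinine is there to catch, and the natural reading already counts that person as not abstinent. The late-nicotine route is built from what the text does not say. The post-test comparison is one that nobody planned: CO is recorded then, but no abstinence rate is defined at that visit. Splitting about four expected abstainers by marker result and nicotine product use, or reporting two rates, would give counts too small to show which rule is nearer the truth.

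**Conclusion.** No change to the plan is needed. The omission is real but is missing detail rather than an error. An analyst would apply accepted cut-offs and require both markers to support the self-report, which is what the outcome sentence and the single cotinine visit point to.

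If the alternative rule were used, each discordant participant would shift the estimate by 3.1 points on a denominator of 32. One or two such cases are smaller than the plan's 9.8-point margin, and the number may be zero. The analysis is descriptive, with no comparator, test or success threshold, so no planned conclusion is shown to change.

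This rests on three assumptions: that the conjunction carries its ordinary meaning, that late nicotine product use is uncommon because the documents do not describe it, and that 32 is the denominator. The effect of different cut-offs remains unquantified, since the documents offer nothing from which to estimate it.

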### **Feasibility Testing**

The intervention that was developed with input from the target audience during the pretesting phase consists of an initial comprehensive assessment (counseling + pharmacologic) since patients tend to come prepared to spend the day at the reference center to get all the needed services. If they are committed to quitting they will proceed with consenting, visits with the Clinical Psychologist and Pulmonologist. The four visits with the Clinical Psychologist can be in person, video or phone based on patient's preferences. Each patient is different and some may require more visits. The Clinical Psychologist will also provide the participant with the opportunity to send and receive texts for support. We will deliver the active intervention following this pattern for three months given the high risk of relapse within the first three months. Then, participants will continue to be engaged for another three months and monthly "check-ins" with the Clinical Psychologist and Pulmonologist. Follow-up assessments will be implemented at 7 months. The **cognitive-behavioral** component is based on evidence-based strategies but tailored to PLWH based on findings of the formative assessments. The tobacco cessation manual is available in Portuguese upon request.

**Pharmacological management** will be consistent with the recommendations and aids available through the public health system in order to assure sustainability – nicotine replacement therapy (NRT) and bupropion (if needed). The optimal dose of NRT can be difficult to determine without evaluating tobacco use pattern, comorbidities, and context. Thus, the NRT dose will be determined based on this evaluation. For example, participants who smoke within 30 minutes of awakening or smoke more than 10 cigarettes daily may be offered a higher dose NRT. (61) Others will receive a lower dose therapy with the option of increasing the dosage if physical withdrawal symptoms persist at 2 weeks. Patches will be initiated one week prior to the quit date, will be administered for 8 weeks total and the dose will be either 21 mg (high dose) or 14 mg (low dose). The dose will not be tapered. Those with skin sensitivities will be offered the alternative of scheduled nicotine gum at 4mg or 2mg doses (which is also offered through the public health system). The appropriate course of treatment will be decided as a collaborative discussion between the participant and the Pulmonologist and the medication will be provided free of charge.

### **Recruitment and Retention Strategies**

The inclusion criteria are: (a) PLWH (that is, patients with a confirmed HIV diagnosis) receiving care at the reference center in Londrina; (b) 18 years of age and older; (c) smoke at

least 5 cigarettes (industrialized or hand-rolled) per day; (d) smoked within the past seven days; and (e) no intent to move from the area served by reference center in Londrina within the next 12 months. Exclusion criteria are a history of hypertension, angina, asthma, or medication for depression.

Participants will be recruited at the reference center with the support from the nursing staff. That is, the nurse will approach the patient who are tobacco users during the visit and ask about their willingness to talk to the Clinical Psychologist to learn more about the program. If they agree, the Clinical Psychologist or Research Assistant will either talk to them that day or call them to explain the study, assure eligibility, and then enroll them the next time they come to the center. Additionally, the introduction brochure described above will also be available at the clinic with the Clinical Psychologist's phone number. In our past studies, we have not provided incentives for participants in a tobacco cessation program since the trial must resemble the real world as much as possible. We will reimburse participants for their expenses associated with transportation and meals for completing assessments (baseline, post-test, 7-month f/u – total R\$150/R\$50 each).

### **Assessments**

Participants will be interviewer-administered baseline, post-test, and 7-month f/u assessments by the Research Assistant since the Clinical Psychologist will be delivering the intervention. Baseline measures will include (those with an \* will also be administered at post-test and 7-month f/u): demographics (e.g., age, income, etc.), tobacco history (e.g., # cigarettes per day, previous attempts, etc.), nicotine dependence\* (Fagerstrom Test for Nicotine Dependence), smoking self-efficacy\* (Smoking Self-Efficacy Scale), depressive symptoms\* (CES-D), and social support.\* These measures have been translated into Portuguese. Exhaled CO levels will be recorded at baseline, post-test, and 7-month f/u. Salivary cotinine will only be assessed at 7-month follow-up.

### **Sample Size and Statistical Analysis**

As this is a feasibility study, sample size is justified based on the measurement precision of parameters referable for larger study. We are estimating sample size based on the results of the meta-analysis of tobacco cessation among PLWH conducted by Pool et al. where cessation was 13% in the intervention group. For the second phase of feasibility testing with 32 participants, we will be 90% confident that true rate of 7-day point prevalence abstinence at 6-months will be between 3.2% and 22.8%. For 90% confidence interval of true mean, we will be able to estimate 0.3 standard deviation as margin of error with sample size of 32. With conservative consideration of 8% attrition rate over 6 months, the study will recruit 40 participants. Descriptive statistics will be presented for participants' characteristics at each time of measures.

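### The verified-abstinence rate is sized on 32 of 40 recruits, which implies a completers' denominator, and no rule says how missing or unverified outcomes are counted.

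*Combined protocol and SAP*

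**What the plan says.** The section Feasibility Testing – Research Protocol names one primary outcome, 7-day point prevalence abstinence at 7 months, "defined as no tobacco use in the past 7 days and verified through measurement of" salivary cotinine and exhaled CO. Under Assessments, CO is recorded at baseline, post-test and 7 months, and cotinine at 7 months only.

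Sample Size and Statistical Analysis holds all the statistical content. It takes a published meta-analysis "where cessation was 13% in the intervention group" as its planning rate. It gives the precision of the abstinence rate on 32 participants ("For the second phase of feasibility testing with 32 participants, we will be 90% confident that true rate of 7-day point prevalence abstinence"), with a stated interval of 3.2% to 22.8% for a 6-month time point. It adds a margin for a mean on the same number ("we will be able to estimate 0.3 standard deviation as margin of error with sample size of 32"). After an attrition allowance of 8%, "the study will recruit 40 participants". The only analysis sentence promises descriptive statistics of participants' characteristics at each measurement time.

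No section states the denominator of the primary rate, or how to classify a participant who withdraws, is lost to follow-up, or has no verifying sample.

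**The concern.** The only number attached to the primary estimate is 32, the number left after an allowance for loss. If everyone enrolled were counted, with missing outcomes classed as not abstinent, attrition would not shrink the denominator and the precision could have been stated on 40. Followed as written, the plan therefore points towards a rate among completers.

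In a cessation programme, loss may well be related to the outcome, because people who have relapsed have less reason to return for a breath and saliva test. Leaving them out treats them as if they quit at the same rate as those who came back. The same gap covers a participant who is still in contact but gives no sample. Counselling need not bring someone to the centre ("The four visits with the Clinical Psychologist can be in person, video or phone based on patient's preferences"), whereas verification needs a physical sample and no earlier cotinine exists to stand in for it.

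The study describes no comparison group, so nothing offsets such a bias, and its estimates are intended to inform a larger study. If the rule is not fixed before outcomes are seen, the same data can support two different primary results.

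**Working it through.** **Inputs** (all from Sample Size and Statistical Analysis): rate 13%, 32 participants for precision, 90% confidence, attrition 8%, 40 recruited.

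**1. The plan's own figures.** The half-width is 1.645 × √(p(1−p)/n). With p = 0.13 and n = 32 it is 9.8 points, giving 3.2% to 22.8%, as stated. The margin for a mean, using the t quantile with 31 degrees of freedom divided by √32, is 0.2997 SD, which matches 0.3.

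**2. Attrition.** 32/(1 − 0.08) = 34.8, so 35 recruits, not 40. In the other direction, 40 × 0.92 = 36.8 would remain, not 32. Going from 40 to 32 is a loss of 8/40 = 20%. The three figures do not agree, so both loss rates are carried below.

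**3. Size of a completers' bias.** Let d be the fraction lost and f the quit rate of the lost relative to those seen. If the rate in all enrolled is 13%, the expected completers' rate is 0.13/(1 − d + f·d).

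| Loss d | Lost never abstinent (f = 0) | Lost quit at half the rate (f = 0.5) |
|---|---|---|
| 8% (stated) | 0.13/0.92 = 14.1% | 0.13/0.96 = 13.5% |
| 20% (32 of 40) | 0.13/0.80 = 16.3% | 0.13/0.90 = 14.4% |

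In the f = 0 column the overstatement is about 1.1 points (9% relative) at 8% loss and 3.3 points (25% relative) at 20% loss. If f = 1, so that loss is unrelated to abstinence, there is none. The values of f are assumptions; the document gives no information on them.

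**4. The same data under two denominators.** Suppose 40 are enrolled, 32 assessed and 5 verified abstinent. Completers: 5/32 = 15.6% (90% Wilson interval 7.8% to 28.8%). All enrolled, missing counted as not abstinent: 5/40 = 12.5% (6.2% to 23.5%). The rate in all 40 could lie anywhere from 5/40 = 12.5% to (5 + 8)/40 = 32.5%. The completers' rate is therefore not an upper bound, and the all-enrolled rate is the lower bound.

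**5. Precision on 40 enrolled, by the plan's formula.**
- If 13% is the rate in all enrolled: half-width 8.7 points, 90% CI 4.3% to 21.7%.
- If 13% applies only to 32 assessed: 0.13 × 32 = 4.16 quitters, 4.16/40 = 10.4%, 90% CI 2.5% to 18.3%.

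**The case against.** The strongest reply is that sizing on an expected evaluable number is an ordinary attrition allowance and does not define an analysis set. That stands. A reader might infer that participants who withdraw or give no sample are removed and that the reported quit rate is therefore inflated. The document does not support this: no section excludes anyone, and any inflation depends on loss being related to relapse. The point is an undefined denominator whose only numerical hint is a completers' number.

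Several further limits also stand.
- The 16.3% figure, a 25% relative overstatement, needs 20% loss. At the plan's stated 8% the worst case in the table is 14.1%.
- Both effects are well inside the plan's own margin of 9.8 points.
- The narrower interval at 40 is not a gain in information. It comes from treating missing outcomes as known.
- The flexible visit format applies to the psychologist's sessions. The assessments are interviews by the Research Assistant, and transport and meals are reimbursed for the 7-month one, which points to attendance. The document does not describe remote reporting of the outcome, so a missing sample in someone still engaged is a possibility to be covered, not a planned route.
- Abstinence is the only named primary outcome, not the only outcome. Dependence, self-efficacy, depressive symptoms and social support are also repeated at follow-up.

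None of this supplies the missing rule.

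**Conclusion.** The point holds as an omission. The plan's one precision statement for the primary rate implies a completers' denominator, and nothing states the denominator or classifies missing or unverified 7-month outcomes. Whether the reported rate will be biased cannot be determined from the document.

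If a completers' rate were used, the true rate in all 40 were 13%, and none of the lost were abstinent, the expected completers' rate would be 14.1% at 8% loss and 16.3% at 20% loss. If the lost quit at half the rate of those seen, it would be 13.5% and 14.4%. These are modest differences against the interval width. They would still carry into the planning of a larger study, and the rule is cheap to fix before outcomes are known. Separately, the 8%, 32 and 40 are inconsistent with each other as written.

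**What to change.** In Sample Size and Statistical Analysis:

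1. Define the primary rate as verified abstinent participants divided by all participants enrolled in the phase being estimated. Say whether the first 10 are included, since the research protocol section allows either a separate phase of 40 or 40 more added to the 10.
2. Count a missing or unverified 7-month outcome as not abstinent, and report deaths separately.
3. Restate the precision on that denominator. For 40 enrolled, the 90% CI is 4.3% to 21.7% if 13% is the rate in all enrolled, or 2.5% to 18.3% if 13% applies only to 32 assessed. Say which is meant.
4. Report the completers' rate as a sensitivity analysis, noting that it is not an upper bound.
5. State that participants who stop treatment are still invited to the 7-month assessment, whose expenses are already reimbursed.
6. Reconcile the 8%, 32 and 40: 8% loss from 32 evaluable needs 35 recruits, while 32 of 40 is 20% loss.

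This takes a few sentences and no new measurements. The downside is that the primary rate may be lower, and is conservative if some of the lost were in fact abstinent.

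### Does the 6-month wording in the sample-size section conflict with a primary outcome measured at 7 months?

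*Combined protocol and SAP*

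**What the plan says.** The opening section, *Feasibility Testing – Research Protocol*, makes 7-day point prevalence abstinence the primary outcome, verified by salivary cotinine and exhaled CO, and places it "at 7-month follow-up (from baseline"). *Feasibility Testing* agrees: "Follow-up assessments will be implemented at 7 months". *Recruitment and Retention Strategies* and *Assessments* both list three assessments: baseline, a post-test with no stated month, and 7 months. *Assessments* schedules CO at all three and cotinine at 7 months only.

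*Sample Size and Statistical Analysis* uses a different month, twice. On precision: "we will be 90% confident that true rate of 7-day point prevalence abstinence at 6-months will be between 3.2% and 22.8" per cent, for 32 participants. On recruitment: "With conservative consideration of 8% attrition rate over 6 months, the study will recruit 40 participants". The section also gives a margin of error for a mean (0.3 standard deviation at 32 participants) and ends: "Descriptive statistics will be presented for participants' characteristics at each time of measures". Neither of these says anything further about abstinence.

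The programme itself lasts six months. First: "We will deliver the active intervention following this pattern for three months". After that: "Then, participants will continue to be engaged for another three months". The quit date is tied only to the start of patches: "Patches will be initiated one week prior to the quit date". No interval from baseline to the quit date is given.

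**The concern.** The sample size is justified wholly by precision, and the 6-month sentence is the only text that attaches a number of participants, a confidence level and an interval to abstinence. No assessment is scheduled at 6 months by that name. Three readings are open:

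- a slip for 7 months;
- six months counted from another origin, such as the quit date;
- the undated post-test, if that falls near the end of the six-month programme.

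The third would matter most. The post-test takes CO but not cotinine, so the stated interval would describe a CO-only rate and the verified primary outcome would have no precision statement.

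The attrition window raises a second worry. If the programme is counted from baseline, scheduled contacts end at month 6. An allowance covering 6 months would then omit the last month before the primary visit, and fewer participants than planned might be evaluable there.

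**Working it through.** **Inputs.** All are from *Sample Size and Statistical Analysis*: abstinence 13%, 32 evaluable, 90% two-sided confidence, 8% attrition over 6 months, 40 recruited. The 7-month time point is from *Feasibility Testing – Research Protocol*.

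**1. Reproduce the stated interval.** The Wald form is p ± z·√(p(1−p)/n) with z = 1.645:

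- √(0.13 × 0.87 / 32) = 0.0594
- half-width = 1.645 × 0.0594 = 0.0978
- interval = 0.13 ± 0.0978 = 3.2% to 22.8%, as stated.

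The formula contains p, n and z and no time term. Writing 7 months in place of 6 leaves the interval as it is, provided 13% and 32 are kept.

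**2. Extend the attrition window by one month.** The document gives no 7-month attrition rate, so assume that the dropout hazard stays constant. Retention at 7 months is then retention at 6 months raised to the power 7/6. The section's own figures support two different 6-month losses, so both are shown.

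| 6-month loss | Left of 40 at 6 months | 7-month loss | Left of 40 at 7 months | Difference |
|---|---|---|---|---|
| 8% (stated) | 40 × 0.92 = 36.8 | 1 − 0.92^(7/6) = 9.3% | 40 × 0.907 = 36.3 | 0.5 |
| 20% (implied: 1 − 32/40) | 32.0 | 1 − 0.80^(7/6) = 22.9% | 40 × 0.771 = 30.8 | 1.2 |

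**3. Effect on precision.** Round down to whole participants and keep 13%.

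- Stated 8%: 36 remain at 6 months and at 7. The half-width is 1.645 × √(0.1131/36) = 9.2 points (3.8% to 22.2%) in both cases, and more than the planned 32 are evaluable.
- Implied 20%: 32 falls to 30. The half-width is 1.645 × √(0.1131/30) = 10.1 points (2.9% to 23.1%), against 9.8 as planned.

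**4. Which outcome does the interval describe?** The sample-size section names 7-day point prevalence abstinence. The protocol defines that term, as its primary outcome, with cotinine and CO verification. Cotinine is collected only at 7 months. The outcome as defined can therefore be measured only at the 7-month visit. No section plans an abstinence rate at post-test; what is scheduled there is CO and the repeated questionnaires.

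**The case for a change.** The strongest case for acting is that 6 months appears twice, in separate sentences, which makes a single mistyped digit less likely. The quit-date explanation is plausible but is nowhere stated. A post-test near month 6 cannot be ruled out either, since the post-test has no date. The estimates are meant to inform a larger study, so the time point should be clear, and making it clear costs only a few words.

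Part of this stands. The wording differs, the difference is unexplained, and a tidy revision would name the time origin. The rest is weaker. The post-test reading is supported only by silence about its date, and it sits badly with the protocol's own definition of the outcome. A larger loss at 7 months can be produced by assuming that the dropout hazard doubles in the final month: 40 × 0.80^(8/6) = 29.7 remain, and the half-width at n = 29 is 10.3 points. Nothing in the document supports that assumption, and even then the change is half a point.

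The wider gap between 36 and 30 evaluable participants does not come from the missing month. It comes from the 8% figure not matching the step from 32 to 40: 32/0.92 = 34.8, so 35 recruits would do, whereas 40 corresponds to a 20% loss. That is a separate discrepancy and should not be counted here.

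**Conclusion.** The 6-month wording is a labelling slip or an unstated clock, and no change to the plan follows. Followed as written, the study still measures cotinine- and CO-verified abstinence at 7 months from baseline. The outcome definition, the visits and the assays all stay the same, and an analyst would set the 7-month result against the stated precision without difficulty.

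The size is nil for the stated interval, given 13% and 32 evaluable. For attrition it is about 0.5 of 40 participants at the stated 8%, or about 1.2 at the implied 20%; at most that adds 0.3 percentage points to the half-width.

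Two assumptions carry this: a constant dropout hazard into month 7, and a 13% rate that applies at 7 months. The document gives no 7-month figure for either. The calculation also takes the number evaluable as the denominator, which the use of 32 suggests, although the plan does not say how participants lost to follow-up are counted.

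### The stated 8% attrition does not take 32 participants to 40 recruits: it gives 35, or leaves about 37 of 40

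*Combined protocol and SAP*

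**What the plan says.** All the relevant figures but one are in the Sample Size and Statistical Analysis section of the combined protocol and SAP.

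- **Number behind the precision.** The section opens its calculation with "For the second phase of feasibility testing with 32 participants". It takes its abstinence rate from a meta-analysis in which "cessation was 13% in the intervention group", and gives a 90% interval of 3.2% to 22.8%. For continuous measures it adds that "we will be able to estimate 0.3 standard deviation as margin of error with sample size of 32".
- **Attrition and enrolment.** It then states: "With conservative consideration of 8% attrition rate over 6 months, the study will recruit 40 participants".
- **Enrolment given elsewhere.** The opening section, Feasibility Testing – Research Protocol, gives 40 for the final pilot without deriving it. It also says that, if the intervention needs no changes after the first 10 participants, the further 40 would be enrolled in Phase II instead.

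No other allowance is described that would link 32 to 40, such as ineligibility after consent, unusable samples or a second stage of loss.

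**The concern.** The attrition sentence is the only stated link between the precision calculation and the enrolment target. It presents 40 as what follows once 8% loss is allowed for. But 8% of a group this size is about three people, whereas 40 exceeds 32 by eight.

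The study is meant to supply planning values for a larger trial, and retention is one of the things such a study informs. If the plan does not say clearly whether it expects 8% or 20% loss, observed retention has no clear figure to be judged against. The printed precision also applies to a number of completers (32) that 8% loss from 40 would not give.

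**Working it through.** **Inputs**, all from Sample Size and Statistical Analysis: n = 32, assumed abstinence p = 0.13, confidence level 90%, attrition d = 8% over 6 months, recruits N = 40.

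**Step 1: confirm that 32 is the number the precision rests on.**

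- Interval for a proportion (Wald): p ± 1.645 × √(p(1 − p)/n) = 0.13 ± 1.645 × √(0.13 × 0.87/32) = 0.13 ± 0.0978, which is 3.2% to 22.8%. This matches the plan.
- Margin for a mean: t(0.95, 31)/√32 = 0.300 SD. With the normal quantile, 1.645/√32 = 0.291 SD. Either rounds to the printed 0.3.

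Both figures reproduce at 32, and attrition is applied afterwards. So 32 functions as the number expected to be available for analysis, although the plan does not use that term.

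**Step 2: inflate 32 for 8% loss.**

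- n/(1 − d) = 32/0.92 = 34.8, so 35 recruits.
- The cruder n × (1 + d) = 32 × 1.08 = 34.6 also gives 35.

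The plan's 40 is 5 more than either formula gives.

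**Step 3: work back from 40.**

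- With 8% loss: 40 × 0.92 = 36.8 remain, not 32.
- Rate that takes 40 to 32: 1 − 32/40 = 20%.
- Allowing for rounding up: 1 − 32/39 = 17.9%, so only rates above 17.9% and up to 20% give 40 recruits.

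**Step 4: see whether another reading of 8% gives 40.**

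- Applied twice: 32/0.92² = 37.8. Applied three times: 32/0.92³ = 41.1. Neither is 40, and the text states a single 8%.
- Stretched in proportion from 6 months to the 7-month follow-up: 8% × 7/6 = 9.3%, and 32/0.907 = 35.3, so 36.

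**Step 5: what the precision would be if 8% and 40 are both right** (same formulas as Step 1, with the t quantile for the mean).

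| Available for analysis | 90% interval around 13% | Half-width (points) | Margin for a mean |
|---|---|---|---|
| 32 (as printed) | 3.2% to 22.8% | 9.8 | 0.30 SD |
| 36 | 3.8% to 22.2% | 9.2 | 0.28 SD |
| 37 | 3.9% to 22.1% | 9.1 | 0.28 SD |

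With the normal quantile, the margin for a mean at 37 is 0.27 SD.

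**The case against.** The strongest reply is that nothing is broken. Recruiting 40 when 35 would do still delivers the stated precision. The plan calls its allowance conservative, and 40 is also given separately in the opening section. On that view all three figures can stand, with five recruits as an unspoken margin. It is true that 32, 8% and 40 are compatible if such a margin exists. But the plan does not mention one, and the word conservative describes the 8%, not the 40. As written, 40 is offered as the result of an 8% allowance, and it is not.

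A second reply is that 8% may be a slip for 8 participants, since 40 − 8 = 32. This is plausible, but the documents do not say so, and it would itself be an error to correct.

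A third concerns the base. If the first 10 participants were pooled with the further 40, the total would be 50, and 8% loss would leave 46. The plan does not say they would be pooled, and 46 is not 32 either. Likewise, counting dropouts as smokers would make the denominator for abstinence 40. No such rule is stated, and it would not give 32.

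What does stand is the point about weight. This is a feasibility study with no hypothesis test and no power claim, so no error rate depends on the figure. If 8% is right, the mismatch is on the safe side. If 20% was meant, the printed precision is exact and only the percentage is wrong.

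**Conclusion.** The point holds, as a minor one. The stated 8% attrition does not yield 40 recruits from 32 participants: it yields 35, or it leaves about 37 of 40. The loss that connects 32 to 40 is 20%, two and a half times the stated rate.

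The target of 40 is adequate on every reading, and the half-width for abstinence changes by less than 1 percentage point. The practical cost is ambiguity about the planned loss rate and the expected number of completers.

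The conclusion rests on two readings of the text: that 32 is the number after losses, which both precision figures support, and that 8% is one overall loss over 6 months, as written. The documents do not settle which of the three figures is mistaken.

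**What to change.** Keep enrolment at 40, say which figures are intended, and make the sentence agree with them:

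1. **If 32 and 40 are intended:** replace the attrition clause with wording such as *Allowing for about 20% attrition (8 of 40), 32 participants are expected to be evaluable.* The precision figures stay as they are.
2. **If 8% and 40 are intended:** restate the precision for about 37 participants, with a 90% interval of about 3.9% to 22.1% and a margin for a mean of about 0.28 SD.
3. **If 32 and 8% are intended:** state that 35 recruits are required and that the other 5, up to 40, are an added margin.

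The cost is one sentence, plus two precision figures under option 2. Enrolment and design do not change under any option.
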